7.5 Criteria for Discontinuation or Withdrawal of a Subject

The primary reason for discontinuation or withdrawal of the subject from the study or study medication should be recorded in the eCRF using the following categories. For screen failure subjects, [Section 9.1.15](#).

1. The subject has experienced a PTE or AE that requires early termination because continued participation imposes an unacceptable risk to the subject's health or the subject is unwilling to continue because of the PTE or AE.
2. Liver Function Test (LFT) Abnormalities
Study medication should be discontinued immediately with appropriate clinical follow-up (including repeat laboratory tests, until a subject's laboratory profile has returned to normal/baseline status) if the following circumstances occur at any time during study medication treatment:
 - ALT or AST $>8 \times$ ULN, or
 - ALT or AST $>5 \times$ ULN and persists for more than 2 weeks, or
 - ALT or AST $>3 \times$ ULN in conjunction with elevated total bilirubin $>2 \times$ ULN or INR >1.5 , or
 - ALT or AST $>3 \times$ ULN with the appearance of fatigue, nausea, vomiting, right upper quadrant pain or tenderness, fever, rash and/or eosinophilia ($>5\%$).
3. Significant protocol deviation. The discovery post-randomization that the subject failed to meet protocol entry criteria or did not adhere to protocol requirements and continued participation poses an unacceptable risk to the subject's health.
4. Lost to follow-up. The subject did not return to the clinic and attempts to contact the subject were unsuccessful. Attempts to reach the subject must be documented.

5. Voluntary withdrawal. The subject (or subject's legally acceptable representative) wishes to withdraw from the study. The reason for withdrawal, if provided, should be recorded in the eCRF.

Note: All attempts should be made to determine the underlying reason for the withdrawal, and, where possible, the primary underlying reason should be recorded (i.e., withdrawal due to an AE).

6. The sponsor, IRB, IEC, or regulatory agency terminates the study.
7. Other.

Note: The specific reasons should be recorded in the "specify" field of the eCRF.

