
Primary Objective:
 
To characterize the safety and tolerability profile of escalating dose levels of CVN766 suspension when administered as a single oral dose or daily oral doses for 7 days in healthy subjects, and to determine the recommended phase 2 dose (RP2D).
	

Secondary Objectives:
 
 To characterize the single-dose PK profile of CVN766 in plasma and CSF To characterize the multiple-dose PK profile of CVN766 in plasma and CSF To assess the effect of food on the bioavailability of CVN766 	

Exploratory Objectives:
 
 To explore possible drug metabolic enzyme and transporter polymorphisms that may contribute to variability in CVN766 PK, pharmacodynamics, or safety 	
	

Subject Population: Healthy male and female subjects 18 to 50 years old
	

Number of Subjects:
 
Each dose cohort: 8 subjects (6 active:2 placebo)
 
Estimated total: 64 subjects
 
(5 single-dose cohorts, 3 multiple-dose cohorts)
	
Number of Sites:
 
1 (Australia)

Dose Level(s):
 
Planned single-dose levels are placebo, 5 mg, 15 mg, 45 mg, 125 mg, and 250 mg CVN766.
 
Planned multiple dose levels are placebo, 45 mg, 125 mg, and 250 mg CVN766.
	
Route of Administration:
 
Oral

Duration of Treatment:
 
Single or daily oral doses for up to 7 days (+7 days as necessary to reach steady-state and as required by Safety Review Group).
	
Period of Evaluation:
 
Screening Period: up to 28 days
 
Treatment Period: 1-7 days (+7 days, as necessary).
 
Food Effect washout period (for select cohort only): at least 14 days
 
Follow-up Period: approximately 14 days
 
Total Duration:
 
 Single-dose cohorts: approximately 6 weeks Food effect cohort: approximately 8 weeks Multiple-dose cohorts: approximately 7 weeks

Main Criteria for Inclusion:
 
Healthy male and female subjects who are 18 to 55 years of age, inclusive and have a body mass index (BMI) between 18.0 and 32.0 kg/m² inclusive at Screening.
 
A complete list of inclusion criteria is provided in Section 7.1.
	

Main Criteria for Exclusion:

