6.3 Premature Termination or Suspension of Study or Investigational Site

6.3.1 Criteria for Premature Termination or Suspension of the Study

The study will be completed as planned unless new information or other evaluation regarding the safety of the study medication indicates an adverse change in the risk profile for the compound, such that the SRG or Institutional Review Board (IRB) considers the risk is no longer acceptable for subjects participating in the study.

In addition, if any of the following occur, further dosing will be withheld until the SRG reviews the relevant data, including unblinded data (if deemed necessary by the SRG request), and will decide whether it is safe to suspend dosing or continue dosing at either the planned or alternative dose levels or decides to prematurely terminate the study:

1. Two or more subjects in any single cohort or across more than 1 cohort experience the same type of serious or Medically Significant event as defined by the Investigator
2. Two or more subjects in any single cohort or across more than 1 cohort experience alanine aminotransferase (ALT) and/or aspartate aminotransferase (AST) elevations $>5 \times$ upper limits of normal (ULN) in the absence of a concomitant bilirubin increase (see point 3 below)
3. One or more subjects in any single cohort or across more than 1 cohort experience ALT and/or AST elevations $>3 \times$ ULN in the presence of a total bilirubin increase $>2 \times$ ULN or an international normalized ratio (INR) >1.5 without findings of cholestasis or other alternate etiology to explain the elevations (i.e., “Hy’s Law cases”)
4. Two or more subjects in any single cohort or across more than 1 cohort experience ALT and/or AST elevations $>3 \times$ ULN with the appearance of fatigue, nausea, vomiting, right upper quadrant pain or tenderness, fever, rash, and/or eosinophilia ($>5\%$).

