16. Subject who regularly use nicotine-containing products (including but not limited to cigarettes, electronic cigarettes, pipes, cigars, chewing tobacco, nicotine patch, or nicotine gum). The casual users may participate but must agree to refrain from the time of Screening for the duration of the study or a positive urine cotinine test at Inpatient Check-in (Day 1).
17. Subject has poor peripheral venous access (defined as more than three failed attempts to cannulate).
18. Subject has donated or lost 450 mL or more of their blood volume (including plasmapheresis) or had a transfusion of any blood product within 45 days prior to Day 1.
19. Subject has an abnormal (CS) ECG at Screening or Inpatient Check-in (Day -1). Entry of any subject with an abnormal (NCS) ECG must be approved and documented by signature by the Investigator or medically qualified sub-investigator.
20. Subject has a supine blood pressure outside the ranges of 90 to 140 mm Hg for systolic and 40 to 90 mm Hg for diastolic, confirmed with repeat per PI discretion, at the Screening Visit or Inpatient Check-in (Day -1).
21. Subject has a resting heart rate outside the range of 40 to 100 bpm, confirmed with repeat per PI discretion, at the Screening Visit or Inpatient Check-in (Day -1).
22. Subject has a QT interval with Fridericia's correction method (QTcF) >450 ms (males) or >470 ms (females) or PR outside the range of 120 to 220 ms, confirmed with one repeat testing at the Screening Visit or Inpatient Check-in (Day -1) Visit.
23. Subject has abnormal Screening or Inpatient Check-in (Day -1) laboratory values that suggest a CS underlying disease or subject with the following lab abnormalities: ALT and/or AST >1.5 the ULN, confirmed with one repeat testing.
24. Subject has a risk of suicide according to the investigator's clinical judgment or has made a suicide attempt in the previous 2 years.

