7.6 Procedures for Discontinuation or Withdrawal of a Subject

The investigator must discontinue a subject's study participation at any time during the study when the subject meets the study discontinuation criteria described in Section 7.5. In addition, a subject may discontinue his or her participation without giving a reason at any time during the study. Should a subject's involvement be terminated, the primary criterion for termination must be recorded by the Investigator. In addition, efforts should be made to perform all procedures scheduled for the Early Termination Visit. Discontinued or withdrawn subjects may be replaced at the Sponsor's discretion.

Participants who withdraw from the study prior to dosing may be replaced. If a participant withdraws after the first dose of study medication or placebo, no replacement will occur.

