The local laboratory will perform all clinical laboratory tests. The results of laboratory tests will be returned to the investigator, who is responsible for reviewing and filing these results. All laboratory safety data will be transferred electronically to the sponsor or designee in the format requested by the sponsor. The investigator will maintain a copy of the laboratory accreditation and the reference ranges for the laboratory used.

Laboratory reports must be signed and dated by the Investigator or sub-investigator, indicating that the report has been reviewed and any abnormalities have been assessed for clinical significance. Subjects will be referred to their primary care physician for follow-up of any clinically significant findings or where the investigator or medically trained sub-investigator deems appropriate.

All CS laboratory abnormalities must be recorded as a PTE/AE in the subject’s source documents and on the appropriate eCRF. A CS laboratory abnormality that has been verified by retesting will

be followed until the abnormality returns to an acceptable level or a satisfactory explanation has been obtained.

If subjects experience ALT or AST $>3 \times$ ULN, follow-up laboratory tests at a minimum, serum alkaline phosphatase, ALT, AST, total bilirubin, GGT, and INR should be performed within a maximum of 7 days and preferably within 48 to 72 hours after the abnormality was found.

(Please refer to Section 7.5 for discontinuation criteria and Section 9.8.3 for the appropriate guidance on Reporting of Abnormal LFT in relation to ALT or AST $>3 \times$ ULN in conjunction with total bilirubin $>2 \times$ ULN).

If the ALT or AST remains elevated $>3 \times$ ULN on these 2 consecutive occasions, the investigator must contact the Medical Monitor for consideration of additional testing, close monitoring, possible discontinuation of study medication, discussion of the relevant subject details and possible alternative etiologies. The abnormality should be recorded as an AE (please refer to Section 9.8.3 Reporting of Abnormal LFT for reporting requirements).

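### On daily dosing, the Section 7.5 liver stop at >5×ULN lasting over two weeks cannot take effect before the last dose, so one subject with an isolated, asymptomatic 5–8×ULN value meets no mandatory individual stop

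*Protocol*

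**What the plan says.** Section 7.5, item 2, requires study medication to be stopped at once "if the following circumstances occur at any time during study medication treatment". Four circumstances follow:

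- ALT or AST >8×ULN.
- ALT or AST >5×"ULN and persists for more than 2 weeks, or".
- ALT or AST >3×ULN with total bilirubin >2×ULN or INR >1.5.
- ALT or AST >3×ULN with one of a list of symptoms or signs, or eosinophilia.

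Section 7.6 makes these binding: the investigator must discontinue the subject "when the subject meets the study discontinuation criteria described in Section 7.5".

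The Study Summary gives the treatment duration as "Single or daily oral doses for up to 7 days (+7 days as necessary to reach steady-state and as required by Safety Review Group"). Exclusion criterion 23 in Section 7.2 bars "ALT and/or AST >1.5 the ULN, confirmed with one repeat testing", at Screening or Day -1.

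Two other provisions bear on the same range of values. Section 6.3.1, item 2, withholds dosing for values >5×ULN without a bilirubin rise, but only when the finding involves "Two or more subjects in any single cohort or across more than 1 cohort experience alanine aminotransferase (ALT) and/or aspartate aminotransferase (AST) elevations" of that size. Section 9.1.12 requires repeat tests after any value >3×ULN. If the elevation is still present on the second occasion, "the investigator must contact the Medical Monitor for consideration of additional testing, close monitoring, possible discontinuation of study medication".

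**The concern.** A persistence requirement longer than the treatment course cannot stop treatment. Read quickly, Section 7.5 gives a graded set of individual liver stops at 3×, 5× and 8×ULN. In the multiple-dose cohorts the middle step does nothing: for one subject with raised enzymes and nothing else, the first mandatory stop is above 8×ULN.

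The protocol also treats the same threshold in two ways. Section 6.3.1 regards >5×ULN, with no duration attached, as grounds to withhold dosing once two subjects have it. The first subject to reach that level meets no equivalent rule.

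This is the first study of CVN766 in humans, in healthy volunteers with no prospect of benefit, and sentinel dosing is not required in the multiple-dose cohorts. At stake is whether a volunteer with a marked, unexplained transaminase rise is taken off daily dosing by rule or only by judgement.

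**Working it through.** **Inputs**

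- Last dose: Day 7 as planned, Day 14 at the latest (Study Summary; Sections 6.1.2 and 6.1.3).
- Persistence required: more than 14 days above 5×ULN, during treatment (Section 7.5).
- Entry limit: 1.5×ULN at Screening and Day -1 (Section 7.2, item 23), so a qualifying elevation should begin after dosing starts.
- First post-dose laboratory draw, multiple-dose schedule in Appendix A: Day 2 by note (f), Day 3 by the grid. The two differ, so both are carried through.

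The protocol gives no figure of its own to reproduce.

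**When the clause can first be true**

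Earliest day = day of first value + 14 + 1.

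| First value >5×ULN | Clause first met | Days after Day 7 | Days after Day 14 |
|---|---|---|---|
| Day 2 | 2 + 15 = Day 17 | 10 | 3 |
| Day 3 | 3 + 15 = Day 18 | 11 | 4 |

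Even an elevation already present pre-dose on Day 1 would meet the clause only on Day 16. One present on Day -1, which exclusion 23 would bar, would meet it on Day 15 (there is no Day 0). In every case the last possible dose has already been given.

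**What the other individual stops do**

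For one subject with normal bilirubin and INR, no symptoms and no eosinophilia, the four liver criteria were applied at elapsed times of 0 to 14 days:

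| ALT or AST (×ULN) | Any mandatory stop? |
|---|---|
| 4 | No |
| 5.1 | No |
| 6 | No |
| 7 | No |
| 8 | No |
| 8.1 | Yes (>8×ULN) |

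**Planned doses that could follow, 7-day course**

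Doses from the day of the pre-dose draw = 7 − day + 1.

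- Day 2 (note f only): 6
- Day 3: 5
- Day 5: 3
- Day 7: 1

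Each count falls by one if the result arrives after that day's dose.

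The 14-day extension is not used for these counts because it looks unlikely. If steady state takes 5 half-lives (an assumption), 6 days (144 h) is too short only when the half-life exceeds 144 / 5 = 28.8 h. Section 6.2 gives up to 6.5 h in animals.

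**Single-dose cohorts**

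S1, S2, S4 and S5 have no second dose to stop. S3 has two. Under the Appendix A footnote the fed period starts about Day 8 + 14 = Day 22, when a Day 2 value would be 22 − 2 = 20 days old, so the clause could be met. Under Section 6.1.1 the minimum return is Day 1 + 14 = Day 15, when the same value would be 13 days old and the clause would not be met. S3 is thus the one place where the clause could act.

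**The case against.** The strongest reply is that the clause was never an immediate 5×ULN stop. It is a persistence rule that tolerates isolated values of 5–8×ULN for two weeks in a trial of any length. On this view the complaint is really that the immediate enzyme-only threshold is 8× rather than 5×, which is a matter of preference. It is true that deleting the clause would change nothing within a 7-day course. But a rule listed as binding during treatment, which treatment is too short to trigger, has no function on daily dosing. Section 6.3.1 shows that the protocol itself treats >5×ULN without persistence as a reason to hold dosing.

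The second reply is that these subjects are closely supervised. They are inpatients through Day 9 with frequent laboratory tests. Section 9.1.12 makes repeat testing compulsory, and Medical Monitor contact too if the elevation persists. Section 7.5, item 1, allows withdrawal for an event judged an unacceptable risk. The Safety Review Group can stop dosing under Section 6.1.3, and the two-subject hold in Section 6.3.1 counts across cohorts, so one earlier case makes the next a study-wide hold. All of this stands and lowers the risk. None of it obliges anyone to stop dosing the first affected subject. The outer limit for the repeat test is 7 days, so a Day 3 value could be repeated as late as Day 10, after the planned last dose, although scheduled draws make an earlier repeat likely.

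Third, no hepatic signal is cited, and the top planned dose of 250 mg is well below the 1670 mg/day stated as the NOAEL equivalent. That is fair: the working shows how long a subject could remain exposed, not how likely the event is.

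Finally, the Day -1 eligibility re-check in the S3 fed period may not include a fresh ALT. The grid leaves the laboratory cell blank there, although note (f) lists Day -1. The clause may therefore have some use in S3, which does not affect the multiple-dose cohorts.

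**Conclusion.** The concern holds, with high confidence, for cohorts M1 to M3 and any added multiple-dose cohort on the same schedule. The clause is first met 10–11 days after the planned last dose and 3–4 days after the latest permitted one. A single subject with an isolated, asymptomatic value above 5× and up to 8×ULN meets no mandatory individual stop. Whether the remaining doses are given is left to judgement.

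This rests on the entry limit being enforced, persistence being counted from the first post-dose value, and dosing not going beyond 14 days. The conclusion is the same under either reading of the Appendix A laboratory schedule. Because discretionary oversight exists, this should be fixed but is not critical.

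**What to change.** In Section 7.5, replace the two-week persistence clause with one that can act within the dosing period. For example: withhold dosing at ALT or AST >5×ULN, and discontinue if the value is confirmed on a prompt repeat or at the next scheduled draw. The sponsor and Safety Review Group should set the exact threshold and confirmation rule. The other liver criteria in Section 7.5, and Sections 6.3.1 and 9.1.12, can stay as they are.

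Acting on the first value could spare up to 6 of 7 planned doses after a Day 2 finding, or 5 of 7 after Day 3.

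The cost is a one-line amendment using tests already scheduled every one to two days during confinement. A subject with a transient rise may lose some remaining doses. Replacement is unclear: Section 7.6 says "If a participant withdraws after the first dose of study medication or placebo, no replacement will occur", but also leaves replacement of discontinued subjects to the sponsor's discretion. If there is no replacement, a cohort could have Day 7 pharmacokinetic data from 5 of its 6 active subjects. The amendment could settle that conflict too.

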7.6 Procedures for Discontinuation or Withdrawal of a Subject

The investigator must discontinue a subject's study participation at any time during the study when the subject meets the study discontinuation criteria described in Section 7.5. In addition, a subject may discontinue his or her participation without giving a reason at any time during the study. Should a subject's involvement be terminated, the primary criterion for termination must be recorded by the Investigator. In addition, efforts should be made to perform all procedures scheduled for the Early Termination Visit. Discontinued or withdrawn subjects may be replaced at the Sponsor's discretion.

Participants who withdraw from the study prior to dosing may be replaced. If a participant withdraws after the first dose of study medication or placebo, no replacement will occur.

8.0 CLINICAL TRIAL MANAGEMENT

8.1 Study Medication and Materials

This section contains information regarding all medication and materials provided directly by the sponsor and/or sourced by other means required by the study protocol, including important sections describing the management of clinical trial material.

8.1.1 Dosage Form, Manufacturing, Packaging, and Labeling

Study drug refers to CVN766 and matching placebo. Study drug will be provided in bulk supply. An unblinded pharmacist will manage and prepare doses as oral suspensions as needed throughout the study.

In this protocol, the term study medication refers to all or any of the drugs defined below.

8.1.1.1 Investigational Drug

CVN766 and Matching Placebo

CVN766 drug substance is supplied as a bulk powder to the clinical site and then compounded into oral suspensions. A matching placebo suspension containing all of the components of the active oral suspension with the exception of the drug substance will also be compounded by the site. Compounding instructions will be outlined in a separate pharmacy manual and provided by the sponsor. See [Table 4](#) for the composition of the drug product and matching placebo suspensions.

The oral suspensions will be labeled with the appropriate study information and caution statements.

Table 4 Composition of CVN766 Oral Suspension and Matching Placebo

Component	CVN766 Oral Suspension (individual dose)					Matchin g Placebo
	5 mg	15 mg	45 mg	125 mg	250 mg	
CVN766 drug substance	5 mg	15 mg	45 mg	125 mg	250 mg	NA
Commercial suspending vehicle ^a	10.0 mL	10.0 mL	10.0 mL	10.0 mL	10.0 mL	10.0 mL

NA=Not applicable;

^a An off-the-shelf commercial suspending vehicle will be used, and the details of the vehicle will be provided in the Pharmacy Manual.

8.1.1.2 Ancillary Materials

Ancillary materials will be provided by either the clinical site and/or the sponsor based on availability.

Ancillary material details are provided in the pharmacy manual.

Unused ancillary materials, if provided by the sponsor, will be accounted for and disposed of as directed by the sponsor or their designee.

8.1.2 Drug Storage

All clinical trial material must be kept in an appropriate, limited-access, secure place until used or returned to the sponsor or designee for destruction.

All study medication must be stored under the conditions specified on the label and remain in the original container until dispensed. A daily temperature log of the drug storage area must be maintained every working day.

CVN766 drug substance is stored at room temperature. CVN766 oral suspension and matching placebo should be stored according to instructions in the Pharmacy Manual.

8.1.3 Dose and Regimen

The investigator or investigator's designee will instruct the subject on dosing procedures.

All dosing will occur while subjects are in the clinic under the supervision of the Investigator and in fed or fasting conditions as outlined in Section 7.4.

The exact time of dose will be recorded in the source documents and on the appropriate eCRF.

The planned dose levels to be studied are provided in Table 5. If the planned highest dose level does not reach the desired exposure, then additional cohorts with higher dose levels may be considered. If all planned dose levels are not tolerated in an earlier cohort, the following cohorts may study lower doses at the discretion of the Investigator and the SRG. The actual choice of the subsequent dose level will occur after a full review of the available blinded safety, tolerability, and clinical laboratory results, and available PK data in the preceding cohort. The subsequent dose level may be higher, lower, or remain the same as the preceding dose level.

Table 5 describes the treatment and medication type that would be provided for each cohort.

Table 5 Planned Single and Multiple Dose Levels by Cohort

Single-Dose Cohorts			
Cohort	Planned Treatment*	No. of Subjects	Medication Type
S1	CVN766 5 mg	6	oral suspension
	Placebo	2	oral suspension
S2	CVN766 15 mg	6	oral suspension
	Placebo	2	oral suspension
S3 Fasted	CVN766 45 mg	6	oral suspension
	Placebo	2	oral suspension
S3 Fed (Same 8 subjects as in the S3 FASTED cohort)	CVN766 45 mg	6	oral suspension
	Placebo	2	oral suspension
S4	CVN766 125 mg	6	oral suspension
	Placebo	2	oral suspension
S5	CVN766 250 mg	6	oral suspension
	Placebo	2	oral suspension
Multiple Dose Cohorts			
Cohort	Planned Treatment*	No. of Subjects	Medication Type
M1	CVN766 45 mg	6	oral suspension
	Placebo	2	oral suspension
M2	CVN766 125 mg	6	oral suspension
	Placebo	2	oral suspension
M3	CVN766 250 mg	6	oral suspension
	Placebo	2	oral suspension

* Dose (active or placebo) is in 10 mL of suspension.

